## 2. GLOSSARY OF ABBREVIATIONS AND DEFINITION OF TERMS

ADR	Adverse drug reaction
AE	Adverse event
ALP	Alkaline phosphatase
ALT	Alanine transaminase
AST	Aspartate transaminase
CHMP	Committee for Medicinal Products for Human Use
CMV	Cytomegalovirus
CRF	Case Report Form
(e)CRF	(Electronic) case report form
DSPH	Drug Safety & Public Health
EAP	Early Access Program
EC	European Commission
ECOG	Eastern Cooperative Oncology Group
EMA	European Medicines Agency
EU	European Union
FL	Follicular Lymphoma
GGT	Gamma-glutamyl transpeptidase
GPP	Good Pharmacoepidemiology Practices (guidelines for)
GSI	Gilead Sciences, Inc.
GVP	Good Pharmacovigilance Practices (guidelines for)
HOI	Health Outcomes of Interest
HREC	Human Research Ethics Committees
IDL	idelalisib
IEC	Independent ethics committee
LDH	Lactate Dehydrogenase
MAR	Missing at random
MCAR	Missing completely at random
MST	Medical Search Term
OS	Overall Survival
PAS	Post-Authorization Study
PASS	Post-Authorization Safety Study
PJP	Pneumocystis jirovecii pneumonia
PML	Progressive Multifocal Leukoencephalopathy
QPPV	Qualified person responsible for pharmacovigilance
SADR	serious adverse drug reaction
SAE	serious adverse event
SmPC	Summary of Product Characteristics

---

SSR	Special situation report
STROBE	Strengthening the Reporting of Observational Studies in Epidemiology
TMF	Trial Master File
US, USA	United States, United States of America
Analytical dataset	The minimum set of data required to perform the statistical analyses leading to the results of the primary objective(s) of the study
Bias	Systemic error in the design, conduct or analysis of a study that results in a mistaken estimate
Cohort	Group of people characterized by a common experience (e.g., occurrence of a specified disease, exposure to a given medication)
Confounder	Extraneous factor that accounts for a difference in disease frequency between the exposure groups; associated factors serving as surrogates for these factors are also commonly called confounders
End of data collection	The date from which the analytical dataset is completely available
Exposure	A variable whose effect is of interest and is being studied
Odds	The ratio of the probability that an event will happen to the probability that it will not happen
Outcome	An event (such as disease occurrence or death) that is studied in relation to exposure
Rate	A measure of event occurrence, calculated by dividing the total number of events by the total amount of person-time within an exposure category
Risk	The proportion of a fixed cohort in which an outcome occurs during a specified period of time
Start of data collection	Date from which information on the first study subject is first recorded in the study dataset

## 4. PROTOCOL SYNOPSIS/ABSTRACT

**Gilead Sciences International Ltd.**  
**[name]**  
**[name]**  
**United Kingdom**

---

Study Title:	Non-interventional study to assess the safety profile of idelalisib in patients with refractory follicular lymphoma (FL)
Rationale and Background:	The Committee for Medicinal Products for Human Use (CHMP) adopted a positive opinion on the Pharmacovigilance Risk Assessment Committee (PRAC) recommendations following their review under Article 20 of the new safety findings for idelalisib. As a condition of the CHMP recommendations, additional safety information concerning the use of idelalisib to treat patients with refractory FL was requested.
Research Question and Objectives:	The objective of this study is to assess the overall safety profile of idelalisib monotherapy in patients with refractory FL. Serious Adverse Events (SAEs) will be collected and according rates will be estimated. Focus will be given to special health outcomes of interest (HOIs) such as transaminase elevation, severe diarrhoea/colitis, pneumonitis, neutropenia, rash, Stevens-Johnson syndrome – Toxic epidermal necrolysis (SJS-TEN) and serious infections (including opportunistic infections such as Pneumocystis jirovecii pneumonia [PJP] and cytomegalovirus [CMV]) as listed in the Zydelig Risk Management Plan (RMP) for the EU (Version 2.0).
Study Design:	
A retrospective cohort study enrolling patients who were or are being treated with idelalisib for refractory FL according to the product information and treatment guidelines in routine clinical practice after the country specific approval date.
 
Patient's data will be collected from the date of treatment initiation with idelalisib until 6 months after treatment discontinuation.
 
The study design allows for both retrospective and prospective data to be collected. The start of data collection is defined as the entry of the first patient into the eCRF. In the data analysis, any data prior to the start of the study will be considered retrospective. Any data after that date will be considered prospective.

---

---

**Population:**

Inclusion criteria:

- Adult patients (age ≥ 18) who were or are being treated for refractory FL according to the product information for idelalisib and treatment guidelines in routine clinical practice.

Exclusion criteria:

- Patients included in clinical trials on idelalisib within the timeframe of this study.

**Variables:**

This is a non-interventional study. Only data available from routine medical practise will be collected within the study. All variables collected will be identical in nature and independent of the method of data collection (retrospective/prospective).

At treatment initiation (baseline):

Demographics

- Gender, year of birth

Baseline Disease assessment

- Organ involvement
- Lymph nodes (bulky disease)
- Bone marrow involvement

Medical history

- Follicular Lymphoma History
  - Date of diagnosis
  - FL Stage 1, 2 or 3a
  - Ann Arbor disease stage
- ECOG Performance Status , if available

Treatment history:

- Prior treatment regimens for FL:
  - Drug names for each regimen
  - Number of cycles or duration that regimen administered
  - Reasons for discontinuation

Idelalisib treatment (start date, dose at baseline)

Co-medications:

- Current medications
- Name of medications
- Indication
- Start date or estimated duration on medication

Routine laboratory parameters and results:

- Hemoglobin, erythrocyte count; total leukocytes, absolute neutrophil count, lymphocytes, monocytes, platelet count
- Serum chemistry including sodium, potassium, urea, uric acid, creatinine, lactate dehydrogenase (LDH)
- Liver function test: ALT, AST, ALP, GGT, total bilirubin, albumin, total protein

*During observation period (visits based on local clinical practice, collected retrospectively and prospectively):*

Collection of SAEs, SSRs, ADRs and SADR (see protocol section 11.1). Focus will be given to special HOIs:

- any grade bowel perforation
- grade 3 diarrhoea and/or colitis
- any grade Progressive Multifocal Leukoencephalopathy (PML)
- any grade pneumonitis
- grade 3 rash by MST
- infection (specifically grade 3 infection, grade 3 febrile neutropenia, grade 3 neutropenia, any grade Cytomegalovirus [CMV] infection, and any grade Pneumocystis jirovecii pneumonia [PJP])
- Transaminase elevation
- Stevens-Johnson syndrome – Toxic epidermal necrolysis (SJS-TEN)

Idelalisib treatment

- Change in idelalisib dose (date), including interruption of dosing and reason
- Co-medications (changes)

Routine laboratory parameters and results (when available):

- Hemoglobin, erythrocyte count; total leukocytes, absolute neutrophil count, lymphocytes, monocytes, platelet count
- Serum chemistry including sodium, potassium, urea, uric acid, creatinine, LDH
- Liver function test: ALT, AST, ALP, GGT, total bilirubin, albumin, total protein

Discontinuation (as defined by stopping treatment for more than 30 days) information

- Date and reason for discontinuation
- In case of death:
  - Date and cause of death

---

**Data Sources:**

The primary data source will be the patient's medical records. Review of electronic or paper medical records and entry of data into the study electronic Case Report Form (eCRF) will be performed by trained site personnel. All data will be anonymised and collected for those patients meeting all eligibility criteria. Each patient will be identified by a unique eCRF generated subject identifier. For the retrospective data, medical record abstraction will be performed by internal study team members of the site, who will be trained on the abstraction method to ensure records are acceptable for review and inclusion in the study. Retrospective data will be entered as close to the start of the study as possible. Prospective data will be entered as close as to the patient's last visit as possible.

**Study Size:**

This study aims to include patients who have been or are currently being treated with idelalisib according to the product information and treatment guidelines in routine clinical practice for the treatment of refractory FL, after marketing authorisation in the EU (September 2014) and Australia (January 2015).

Assuming a median treatment period of 8 months, a retrospective timeframe of around 3 years and a prospective observation period of 2.5 years, it is expected that data of approximately 300 patient-years will be collected.

Patients will be identified and enrolled in Europe (pending outcome of study feasibility: Australia, Austria, Belgium, France, Germany, Greece, Ireland, Italy, Portugal, Spain, Sweden, Switzerland and the United Kingdom) and Australia.

---

**Data Analysis:** Continuous variables will be summarized by mean, standard deviation, median, lower quartile, upper quartile, minimum and maximum. Categorical variables will be summarized by number and percentage of patients in each categorical definition including 95% confidence intervals.

Multivariate Poisson regression analyses will be used to estimate adjusted rates of ADRs and SADR.

Multivariate Cox Proportional Hazard analyses will be used to model time-to-event data, and time to ADRs and SADR.

Kaplan Meier will be used to illustrate time-to-event analyses.

Stratified analyses will be used to account for potential behavioral changes of the site staff after the initiation of the study that might introduce bias between retrospective and prospective data collection.

**Milestones:**

Start of data collection:	Q1 2018
End of Data collection:	Q3 2020
Interim report:	Q1 2019
Progress report:	Q1 2019
Final Study report:	Q4 2020

---

This study will be conducted in accordance with the guidelines of Good Pharmacoepidemiology Practices (GPPs) and Heads of Medicines Agencies (HMA) Good Pharmacovigilance Practices (GVP) including archiving of essential documents.

## 5. AMENDMENTS AND UPDATES

This is the updated protocol version 1.1.

Amendment or Update Number	Date	Section of Study Protocol	Amendment or Update	Reason
1.1	13 June 2017	The entire protocol was updated.	1.1	Incorporating PRAC feedback.

- **Protocol Modifications**

Protocol modifications may only be made by Gilead Sciences. Approval must be obtained before changes can be implemented.

## 6. MILESTONES

Milestone	Planned Date
Start of data collection	Q1 2018
End of data collection	Q3 2020
Study interim report on retrospective data analysis	Q1 2019
Study progress report	Q1 2019
Final report of study results	Q4 2020

## **7. RATIONALE AND BACKGROUND**

### **7.1. Rationale for the Current Study**

An increased risk of death and a higher incidence of serious adverse events (SAEs, predominantly infectious events) among subjects receiving idelalisib in combination with standard regimens compared to the control groups were observed in three Phase 3 studies evaluating treatment in first-line CLL and early-line iNHL patient populations by an independent data monitoring committee. The European Commission (EC) was notified of these findings and a review of these data was conducted by the Pharmacovigilance Risk Assessment Committee (PRAC) under Article 20 of Regulation (EC) No 726/2004. This review assessed the impact of these findings on the risk-benefit balance of Zydelig (idelalisib) in the approved EU indications. The PRAC review concluded that the risk-benefit profile for idelalisib remained positive for approved indications, with some updates to the indication and introduction of warnings and precautions in the Summary of Product Characteristics (SmPC) for risk minimization measures to minimize the risk of serious infections.

The risk-benefit balance of idelalisib monotherapy for the treatment of patients with follicular lymphoma (FL) that are refractory to 2 prior lines of treatment was considered to remain positive provided that the agreed risk minimization measures are applied. However, as no controlled study was conducted in this indication, the PRAC required Gilead to collect additional safety data in patients with refractory FL in order to better describe the safety profile of idelalisib in this population.

## **8. RESEARCH QUESTIONS AND OBJECTIVES**

The primary objective of this study is:

To assess the overall safety profile of idelalisib monotherapy in patients with refractory FL.

Serious Adverse Events (SAEs) will be collected and according rates will be estimated. Focus will be given to special health outcomes of interest (HOIs) such as transaminase elevation, severe diarrhoea/colitis, pneumonitis, neutropenia, rash, Stevens-Johnson syndrome – Toxic epidermal necrolysis (SJS-TEN) and serious infections (including opportunistic infections such as *Pneumocystis jirovecii* pneumonia [PJP]) and cytomegalovirus [CMV] as listed in the Zydelig Risk Management Plan (RMP) for the EU (Version 2.0).

## **9. RESEARCH METHODS**

### **9.1. Study Design**

A retrospective cohort study enrolling patients who were or are being treated with idelalisib for refractory FL according to the product information and treatment guidelines in routine clinical practice after the country specific approval date.

Patient's data will be collected from the date of treatment initiation with idelalisib until 6 months after treatment discontinuation.

The study design allows for both retrospective and prospective data to be collected. The start of data collection is defined as the entry of the first patient into the eCRF. In the data analysis, any data prior to the start of the study will be considered retrospective. Any data after that date will be considered prospective.

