### **9.2. Setting**

The study will be conducted in the following countries (pending outcome of study feasibility): Australia, Austria, Belgium, France, Germany, Greece, Ireland, Italy, Portugal, Spain, Sweden, Switzerland and the United Kingdom.

Countries selected for this study include those in which an Early Access Program (EAP) for idelalisib in refractory FL patients has been running since the time of marketing authorisation (MA) for idelalisib. Additional countries without an active EAP were included based on the volume of idelalisib prescribing since the time of the MA. Sites within these countries will be selected based on whether they have been prescribing idelalisib for refractory FL patients in accordance with the approved product information for idelalisib. Final number of sites per country will depend on the available number of patients per site.

The study is expected to last 36 months from the start of data collection (Q1 2018) until submission of the CSR (Q4 2020).

Inclusion criteria:

- Adult patients (age ≥ 18) who were or are being treated for refractory FL according to the product information for idelalisib and treatment guidelines in routine clinical practice.

Exclusion criteria:

- Patients included in clinical trials on idelalisib within the timeframe of this study.

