### **9.5. Study Size**

This study aims to include patients who have been or are currently being treated with idelalisib according to the product information and treatment guidelines for the treatment of refractory FL after marketing authorization in the EU (September 2014) and Australia (January 2015).

Prevalence data for iNHL in the EU are limited. HAEMACARE, a European cancer registry-based project on hematologic malignancies funded by the European Commission, provides European incidence rates but not prevalence data {Sant 2010}. Australian prevalence data could not be identified. The Decision Resources Group (<http://www.decisionresourcesgateway.com/index.aspx>) estimated a 10-year limited-duration prevalence for FL in 5 major EU countries (France, Germany, Italy, Spain, and United Kingdom) over the 2011-2021 forecast period based on cancer registry databases in the EU-5. The EU prevalence estimates for FL ranged from 1.4 (Spain) in 2011 to 3.1 (France) per 10,000 in 2015 (RMP, section 1.1.1.4.2).

Based on the pivotal studies 101-09, GS-US-313-0124 and GS-US-313-0125 the median treatment period is estimated to be 8 months, taking into account that studies GS-US-313-0124 and GS-US-313-0125 were terminated early. Thus, a retrospective timeframe of around 3 years and a prospective observation period of another 2.5 years allow data of approximately 300 patient-years to be collected.

A sample size of 300 patient-years is based on the chance to find a proportion of adverse events of 3.2% with a precision of 2%. The table below shows the relationship between various detectable single proportions of AEs and precision of the estimate.

Proportions found in studies 101-09, GS-US-313-0124 and GS-US-313-0125 were 1.4% ( Grade 3 diarrhea and/or colitis), 2.0% (( Grade 3 febrile neutropenia), 6.1% (( Grade 3 infection) and 8.1% (( Grade 3 rash).

Proportion of AEs	3.2%	5.2%	7.6%
Precision	0.02	0.025	0.03

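### Cohort entry follows treatment rather than first dose after approval, and the undated trial exclusion removes whole patients; both can distort event rates, by an unknown amount

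*Protocol*

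**What the plan says.** Three places in the protocol define who enters.

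- Section 9.1 describes a cohort of past and current idelalisib users whose treatment follows the label and "treatment guidelines in routine clinical practice after the country specific approval date". The follow-up rule is: "Patient's data will be collected from the date of treatment initiation with idelalisib until 6 months after treatment discontinuation".
- The inclusion criterion in Section 9.2 reads "Adult patients (age ≥ 18) who were or are being treated for refractory FL according to the product information for idelalisib", followed by treatment guidelines in routine practice. It contains no date and no condition on when idelalisib was started.
- Section 9.5 aims at patients who "have been or are currently being treated with idelalisib according to the product information and treatment guidelines", and attaches this to marketing authorisation (EU September 2014, Australia January 2015). Here too the date qualifies treatment, not its start.

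The only exclusion, in Section 9.2, is "Patients included in clinical trials on idelalisib within the timeframe of this study". The timeframe is not given dates. Section 9.1 states that "any data prior to the start of the study will be considered retrospective", and Section 9.2 counts 36 months from the start of data collection in Q1 2018, which together suggest a study running 2018 to 2020. Section 9.5, however, also speaks of a retrospective timeframe of about 3 years, which suggests a window reaching back to roughly the approval dates.

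**The concern.** A safety cohort needs eligibility, time zero and the start of risk time to coincide. Here eligibility can be met at approval while risk time begins at the first dose. Take two patients who start on the same day before approval. One dies or stops for toxicity before approval, is never treated after it, and does not qualify. The other continues into routine care, qualifies, and contributes the whole period back to the first dose. That pre-approval period cannot contain a death or a treatment-ending event, because such an event would have prevented entry.

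The exclusion raises a different problem. It acts on the patient, not on the time spent in the trial. A patient who starts in routine care, accrues months of follow-up and perhaps events, and then joins an idelalisib trial inside the window is removed completely. Eligibility then depends on something that happens after entry.

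The regulator asked for this study because no controlled data exist in the indication (Section 7.1). Its outputs are event rates, Poisson and Cox models and Kaplan-Meier curves (Sections 8 and 9.7), and all of them depend on a sound time zero.

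**Working it through.** **No figure in the plan is in dispute.** The protocol gives no number of pre-approval starters or of later trial entrants. The precision table in Section 9.5 is useful only as a yardstick. With 300 units, 1.96 × √(p(1−p)/300) gives 0.0199, 0.0251 and 0.0300 at 3.2%, 5.2% and 7.6%, matching the stated 0.02, 0.025 and 0.03.

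**Inputs**

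- Median treatment period: 8 months (Section 9.5).
- Exponential treatment time: assumed. Mean m = 8/ln 2 = 11.54 months.
- Share f of the cohort that started before approval: not in the documents; assumed 2% to 20%.
- Lead time L between first dose and approval: not in the documents; assumed 3 to 12 months.

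**Step 1: how selective survival to approval is.** The proportion still on drug after t months is exp(−ln 2 × t/8): 0.595 at 6 months and 0.354 at 12 months.

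**Step 2: effect on the rate of a treatment-ending event.** Under the exponential assumption a carry-over patient contributes L event-free months and then, on average, m further months. Every other patient contributes m. Hence

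naive rate / true rate = m / (m + f × L).

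| f | L (months) | f × L | Ratio | Relative understatement |
|---|---|---|---|---|
| 2% | 3 | 0.06 | 0.995 | 0.5% |
| 5% | 6 | 0.30 | 0.975 | 2.5% |
| 10% | 12 | 1.20 | 0.906 | 9.4% |
| 20% | 12 | 2.40 | 0.828 | 17.2% |
| 0% | any | 0 | 1 | 0 |

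Counting the 6-month post-treatment window as well, the event-free share f × L / (m + 6 + f × L) is 0.3% in the first row and 12.0% in the fourth.

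**Step 3: scale against the planned precision.** As a rough guide, 3.2% × 0.975 = 3.12% and 3.2% × 0.828 = 2.65%. The shifts of 0.08 and 0.55 percentage points are both smaller than the planned half-width of 2 points.

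**Step 4: early period.** If every event of a given type ends treatment and falls within the lead time, the early proportion p becomes p(1−f). For the 8.1% quoted in Section 9.5 for rash, that is 7.7% at f = 5% and 6.5% at f = 20%.

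**Step 5: the exclusion under its two readings.** No arithmetic is possible, so the consequences are set side by side.

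| Reading of the timeframe | Earlier trial participants | Routine-care patient who later joins a trial |
|---|---|---|
| 2018 to 2020 | Participation before 2018 is not excluded | Removed entirely if joining in 2018 to 2020 |
| Retrospective window included | Participation after the window opened is excluded; participation that ended before it is not | Removed entirely if joining at any time in the window |

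Whole-patient removal on a later event occurs under both readings. Its direction is unknown: dropping patients who had tolerated the drug would raise rates, and dropping patients with events would lower them.

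**The case against.** The strongest reply is that the wording can be read to exclude pre-approval use altogether. Treatment before approval could hardly follow approved product information, trial treatment is not routine practice, and Section 9.2 describes the early access programmes as running since authorisation, not before it. Section 9.3 also limits collection to data from routine care. This reading is reasonable and may well be the intended one. But a carry-over patient meets the on-label, routine-care condition from approval onward, the follow-up rule still reaches back to initiation, and sites in up to 13 countries should not have to infer the cut-off.

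It can also be said that risk-time and censoring rules belong in a statistical analysis plan. For delayed entry this is fair, since Section 9.3 records the treatment start date. It does not help with the exclusion: patients kept out of the eCRF cannot be restored in the analysis.

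A reader might infer three stronger things, none of which the documents support.

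- *The cohort in general selects patients who tolerate the drug.* Past as well as current treatment qualifies, Section 9.7 finds retrospective patients by systematic search, and Section 9.9 generally waives consent for deceased and retrospectively identified patients in order to avoid a survivor cohort.
- *Pre-approval starters are known to be in the cohort, and the 41% (1 − 0.595) to 65% (1 − 0.354) of them who had stopped are lost from it.* No such patients are documented, and those who stopped before approval are outside a post-approval target population.
- *Every safety event is suppressed in the carried-over time.* Only death and treatment-ending events are. Discontinuation means more than 30 days off drug, so events handled by dose change or shorter interruption remain visible.

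**Conclusion.** The point holds as a defect of wording with a possible bias attached, not as a demonstrated bias. Followed literally, the entry and collection rules can admit event-free time for pre-approval starters, and the exclusion can delete a routine-care patient because of a later event.

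The size is unknown. For the first problem it lies between zero, if nobody started before approval, and an understatement of about 0.5% to 17% relative across the assumed ranges. These figures rest on exponential treatment time with an 8-month median, on assumed values of f and L, and on events that end treatment. For the second problem neither size nor direction can be given, because the number of later trial entrants is not stated. The correction is worth making because it is cheap and because patients excluded at entry cannot be recovered afterwards.

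**What to change.** 1. In Sections 9.1, 9.2 and 9.5, require that the first idelalisib dose was given in routine practice on or after the country-specific approval date. Alternatively, keep earlier starters but begin risk time at the later of initiation and approval, with time since first dose retained as the scale in the Cox and Kaplan-Meier analyses.
2. Replace the undated exclusion with idelalisib exposure in a clinical trial before the first routine-care dose.
3. Keep patients who later enter an idelalisib trial, censor them on the date of trial entry, and report how many there are so that readers can judge whether the censoring could be informative.
4. Add a yes/no field for prior idelalisib exposure to the eCRF. Prior lymphoma regimens are already listed by drug name in Section 9.3, but an explicit field removes doubt.

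The cost is criterion wording and one eCRF field. A few carry-over patients may be lost, partly offset by the person-time kept before later trial entry.
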